The primary objective of our study is to determine the efficacy of combined topical cysteamine cream with a 1927 diode non-ablative laser (Clear + Brilliant Permea®; Solta Medical, Inc.), compared to topical cysteamine alone in the treatment of melasma. This efficacy will be assessed using modified Melasma Area and Severity Index (mMASI) scores, a validated physician assessment tool, at baseline and at follow up visits at week 4, 8 and 12 as well as Investigator Global Assessments. Secondary objectives also include an assessment of patient satisfaction which will be evaluated via patient questionnaires distributed to patients at baseline and at week 12. In addition, impact on quality of life will also be assessed utilizing the melasma quality of life scale (MELASQoL) questionnaire which will be administered to patients at baseline and at week 12.

Multiple studies have demonstrated the efficacy of topical cysteamine in the treatment of melasma. Mansouri et al. conducted a double-blind, randomized, controlled clinical study, which included 50 melasma patients, and demonstrated significant efficacy of topical cysteamine in the treatment of melasma. One comparative trial demonstrated that topical 5% cysteamine, though safe and well-tolerated, was less effective than topical 4% hydroquinone in the treatment of facial melasma; however, a later published response indicated that the concentration of cysteamine may have been less than the reported 5%. A single-blind, randomized comparative trial of 54 melasma patients found no statistically significant difference in the efficacy of topical cysteamine compared to topical tranexamic acid; however, cysteamine was better tolerated amongst the patients. Finally, Karrabi et al. also found that cysteamine 5% cream showed greater efficacy than the gold standard, modified Kligman's formula, in their randomized, double-blind trial of 50 patients with epidermal melasma.

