We hypothesize that addition of 1927-nm fractional low-powered diode laser therapy to topical 5% cysteamine will result in significantly greater improvement in both the clinical appearance of melasma as well as patient satisfaction, compared to topical cysteamine alone. Specifically, we hypothesize:

- 1) Patients will experience improvement in their melasma on both treated sides, with greater improvement noted with combined topical and 1927-nm fractional low-powered diode laser treatment noted on their mMASI scores at weeks 4, 8 and 12.
- 2) Patients will report improvement in satisfaction on patient questionnaires on both treated sides, however there will be greater change in satisfaction noted with combined topical and 1927-nm fractional low-powered diode laser treatment at week 12 compared to baseline (week 0)

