**Objectives:**

- A. To evaluate the efficacy of the Clear & Brilliant Permea laser system in combination with topical cysteamine
  - a. To assess for improvement of melasma after completion of three treatments as determined by the treating clinician and objective measures
  - b. To evaluate subject's satisfaction with melasma treatment and assessment of improvement after three treatments
  - c. To evaluate the length of treatment.
- B. To evaluate the safety of melasma treatment in all skin types using the Clear & Brilliant Permea laser in combination with topical cysteamine
  - a. To evaluate the immediate response to treatment
  - b. To evaluate the subject's assessment of comfort associated with treatments
  - c. To determine the rate of adverse events for the treatment group as a whole

**Study Design:** Single Center, Prospective, With Before-After Analysis

**Study population:** Twenty healthy male or female patients, 18-74 years of age, of all skin types with melasma on the face that wish to be treated. Each subject will receive topical cysteamine cream which they will be instructed to use once a day at home. In addition, one side of the face will be randomly selected for treatment with laser. Patients will receive three monthly treatments, at 4-6 week intervals, on the selected side of the face with the Clear & Brilliant Permea laser. The treatment duration including pre and post treatment procedures is estimated to be 90 minutes per subject. Subjects will return for a follow-up visit 3 months after the initial treatment for a total of four visits. The treatment plan will be the same regardless of the subject's skin type. Four passes, at high setting will be performed.

During the first and fourth visit, the areas of treatment will be photographed with a digital camera under controlled conditions. Subject improvement will be assessed via investigator and subject grading at visit 1 and 4. Improvement in melasma will be assessed by blinded evaluators who will review pre and post treatment photographs taken with VISIA® Skin Analysis System for facial imaging (Canfield Scientific Inc) from visit 1 and 4. Side effects (including pain, redness, dryness, and hyperpigmentation) will be assessed and recorded at visits 2, 3, 4.

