#### Sample Size Calculation:

A sample size is calculated to test the null hypothesis with a one-sided paired t-test for simplicity, although the final analysis may employ a statistically more powerful model.

We calculate that for a two-sided alpha level of 5%, a sample size of 20 subjects will enable us to test the null hypothesis with 80% power. In order to enable the analysis and take into account the potential for dropout we may include up to 25 patients.

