**Criteria of Evaluation (Study Endpoints):**

In person assessment by treating physician and photographic assessment in which blinded dermatologists compared photographs of the individual's face areas at baseline and visit 4 from all patients in the study.

Clinical Endpoints:

- In person assessment by treating physicians will measure change in mMASI of the subjects face at between baseline (visit 1) and week 4.
- The Global Aesthetic Improvement Scale (GAIS), a 5-point scale rating global aesthetic improvement in appearance, compared to pretreatment, as judged by the investigator and the subject will also be assessed. The rating categories used on this scale will be “worse” “no change” “improved” “much improved” and “very much improved”. The percent ranking improvements in the Investigator and Subject GAIS scale from baseline (visit 1) to visit 4 will be compared.
- Photographic assessment by two blinded dermatologists will measure changes will assess improvement in melasma by mMASI score. In addition, an investigator quartile improvement score from baseline to week 12 (0 – 0%, no improvement; 76%-100% - very significant improvement) will be assessed.

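### The GAIS sentence commits to comparing percentages, most naturally percent improved; this would be insensitive if both sides improve to different degrees, and a within-patient comparison on the ordered grades should replace it

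*Protocol*

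**What the plan says.** Protocol, Criteria of Evaluation (Study Endpoints), Clinical Endpoints, describes GAIS as "a 5-point scale rating global aesthetic improvement in appearance, compared to pretreatment, as judged by the investigator and the subject". It lists the grades: "The rating categories used on this scale will be “worse” “no change” “improved” “much improved” and “very much improved". Three of the five are degrees of improvement. The analysis is then fixed in one sentence: "The percent ranking improvements in the Investigator and Subject GAIS scale from baseline (visit 1) to visit 4 will be compared". No threshold is given, no rating by side is stated, and no test is named.

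Three other places show what GAIS has to inform:

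- The primary objective (Background) assesses the combination "compared to topical cysteamine alone in the treatment of melasma".
- Under Study population, "one side of the face will be randomly selected for treatment with laser", so each patient supplies a lasered and a cysteamine-only side.
- Hypothesis 1 (Background) reads "Patients will experience improvement in their melasma on both treated sides, with greater improvement noted with combined topical and 1927-nm fractional low-powered diode laser treatment". It goes on to tie this to mMASI scores at weeks 4, 8 and 12.

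**The concern.** If both sides improve, the benefit added by the laser appears mainly as a higher grade of improvement and less as a move from unimproved to improved. A percentage of patients rated improved sees only the second kind of difference. A patient graded *improved* on the cysteamine-only side and *very much improved* on the lasered side counts as a tie, and *worse* is pooled with *no change*. The better cysteamine works alone, the nearer both percentages come to 100% and the less the comparison can show.

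At stake is the GAIS result alone: it could show no difference between sides although the laser adds benefit that the ratings themselves recorded. Among the listed clinical endpoints, GAIS is the only one that the subject rates.

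**Working it through.** **1. What each reading keeps.**

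| Reading of the GAIS sentence | Grades kept | Order used | Pairing used |
|---|---|---|---|
| Percent improved or better | no, three merged | no | not stated |
| Percent in each grade | yes | no | no |
| Paired comparison on the five grades | yes | yes | yes |

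An extreme case shows the first row. Suppose all 20 patients are *improved* on the cysteamine-only side and *very much improved* on the lasered side. Percent improved is 100% against 100% with no discordant pairs, yet all 20 pairs favour the laser.

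**2. The plan's own figure.** Sample Size Calculation gives 20 subjects, 80% power and a two-sided 5% level, but calls the test a "one-sided paired t-test for simplicity". It gives no effect size or SD, so the 20 cannot be reproduced. It can be solved for the standardised paired difference that it implies:

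- Two-sided: (1.960 + 0.842)/√20 = 0.626 by normal approximation; 0.660 by exact noncentral t.
- One-sided: (1.645 + 0.842)/√20 = 0.556 by normal approximation; 0.577 by exact noncentral t.

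That calculation does not concern GAIS. The two exact values serve here only as a plausible effect size.

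**3. Assumed model.** None of these inputs is in the protocol. Each side has a latent normal improvement with SD 1 and between-side correlation ρ. The lasered side is shifted by d × √(2(1 − ρ)), with d = 0.577 or 0.660; at ρ = 0.5 the factor is 1, so the shift equals d. On the cysteamine-only side a share p is improved or better. In the runs tabulated below, 5% are worse and the improved share is split 50/35/15 over its three grades. There are 20 pairs and tests are two-sided at 5%.

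**4. Power at d = 0.660, ρ = 0.5 (6,000 simulated trials per row).**

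| p | Signed-rank on grades | Uncorrected McNemar | Exact McNemar |
|---|---|---|---|
| 50% | 68% | 44% | 30% |
| 60% | 71% | 42% | 25% |
| 70% | 72% | 35% | 15% |
| 80% | 70% | 25% | 6% |

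**5. Range.** Over d = 0.577 and 0.660, ρ = 0.3 to 0.7 and p = 40% to 80%, power is about 47% to 73% for signed-rank, 16% to 50% for uncorrected McNemar and 2% to 40% for exact McNemar. Separate runs agree to within a few points. At the setting kindest to percent improved (d = 0.660, ρ = 0.3, p = 40%), one run gave 53% for uncorrected McNemar against 70% for signed-rank. That gap of 17 points was the smallest at d = 0.660.

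**6. Check with other inputs.** With different grade splits, shifts of 0.6 and 0.8 SD and ρ of 0.3 and 0.6 (d from 0.6/√1.4 = 0.51 to 0.8/√0.8 = 0.89), power was:

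- p = 40%: signed-rank 48% to 89%, exact McNemar 24% to 50%.
- p = 80%: signed-rank 51% to 91%, exact McNemar 5% to 9%.

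With no shift, signed-rank rejected in 4% to 5% of trials, so its advantage is not bought with excess false positives. Exact McNemar rejected in under 2%, so part of its shortfall is conservatism and the uncorrected test is the fairer comparator.

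**7. Why it happens.** At d = 0.660, ρ = 0.5 and p = 70% to 80%, 40% to 46% of patients are improved on both sides but in different grades. About 4 to 5 of the 20 pairs remain discordant. Exact McNemar needs at least 6, all in one direction: 2 × 0.5⁵ = 0.063, 2 × 0.5⁶ = 0.031.

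**The case against.** The strongest reply is that the protocol never writes the cut. It sets no threshold and defines no responder. The wording about ranking directly follows a list of five named categories, so a percentage at each grade is a fair reading and would keep them all. This stands in part. A reader might infer that the plan definitely collapses GAIS and discards all between-side information. The text does not support that: the wording is ambiguous, and even a percent improved retains some of the difference. The per-grade reading does not rescue the sentence, however, because it still names neither an ordered nor a within-patient comparison.

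It also stands that GAIS is not said to be rated or compared by side; the sentence could be taken as investigator against subject, or as change from baseline. The power figures apply once the sides are compared. Hypothesis 1 is stated for mMASI, so carrying its pattern over to GAIS is an inference, though a reasonable one for two ratings of the same melasma.

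Choosing among paired ordinal tests may properly be left to an SAP. Here, though, the protocol has already committed GAIS to a comparison of percentages, and that commitment is the point at issue.

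**Conclusion.** The point holds in limited form. The sentence commits GAIS to percentages. Its most natural reading is insensitive where the trial's own hypothesis places the difference, and its alternative reading ignores order and pairing. Under the assumed inputs the paired ordinal analysis was more powerful in every setting tried, most clearly when cysteamine alone improves many sides. The size of the gain depends on GAIS rates, a between-side correlation and an effect size that the protocol does not supply; the direction did not change over the ranges examined.

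A reader might go further and infer that a null GAIS result would undermine the trial's main conclusion. The protocol does not support that. GAIS is assessed in addition to mMASI, and a photographic quartile improvement score is listed separately, so the consequence is confined to what can be concluded from GAIS.

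**What to change.** Replace the GAIS analysis sentence with:

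> GAIS will be rated for each side of the face at visit 4, and the lasered side will be compared with the cysteamine-only side within patient on the full five-grade ordered scale (for example the Wilcoxon signed-rank test), separately for investigator and subject ratings. The percent in each grade will be shown by side as description.

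This needs no extra patients, visits or raters. If the case report form now holds one whole-face grade, each rater would record two grades at visit 4. The small downside is a headline result that is less simple to state than a percent improved; the descriptive percentages largely make up for it.

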**Laser Parameters:**

Following 15 minutes of topical 30% lidocaine application, patient's side of face that will be treated with Clear & Brilliant 1927nm at treatment level high, with total of 4 passes.

The investigator, the subject, and anyone else in the laser treatment room will wear the appropriate protective eyewear.

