**Intended Use of the Data:**

The expected end use of the data collected will be for the purpose of best practices in treating melasma on the face. As the purpose of the study is to evaluate the safety and efficacy of low energy diode 1927nm, follow-up photos will be examined for melasma improvement by both the investigator(s) and blinded dermatologist reviewers. A satisfaction questionnaire will be given to patients one month after the final laser treatment. Photos and the satisfaction questionnaire will be examined by the principal investigator and sponsor to determine best practices for use of low energy diode 1927nm in treating melasma in face.

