**Clinical Evaluations:**

The following clinical evaluations will be performed throughout the study as detailed in the visit procedure summary. In the event a treatment is to be administered at a visit the scoring should be done before any laser therapy or drug application. The same investigator should complete the evaluations for a given subject throughout the study. If this becomes impossible a sub investigator with overlapping experience with the subject and the study should complete the evaluations.

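### The quartile improvement score sits in the blinded-reader endpoint but is given to an investigator whom nothing masks to the lasered side

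*Protocol*

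**What the plan says.** The lead-in to Criteria of Evaluation (Study Endpoints) sets in-person assessment by the treating physician beside "photographic assessment in which blinded dermatologists compared photographs of the individual's face areas at baseline and visit 4". The third clinical endpoint begins "Photographic assessment by two blinded dermatologists will measure changes will assess improvement in melasma by mMASI score" and then, as an addition within the same bullet, lists "an investigator quartile improvement score from baseline to week 12". No masking is attached to that second item. The bullet also does not say from what material the score is given, or whether each side of the face is scored.

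Other sections bear on who the rater is:

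- The Study population text under Objectives states: "Improvement in melasma will be assessed by blinded evaluators who will review pre and post treatment photographs". It also plans a separate grading: "Subject improvement will be assessed via investigator and subject grading at visit 1 and 4".
- Intended Use of the Data states: "follow-up photos will be examined for melasma improvement by both the investigator(s) and blinded dermatologist reviewers".
- Laser Parameters states: "The investigator, the subject, and anyone else in the laser treatment room will wear the appropriate protective eyewear".
- Clinical Evaluations states: "The same investigator should complete the evaluations for a given subject throughout the study".

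**The concern.** This is a split-face trial. One randomly chosen side is lasered and each subject uses cysteamine, so a rater who knows the lasered side knows the treatment. A percentage-improvement judgement is subjective. If the rater expects the laser to help, that expectation enters the difference between the sides with nothing to offset it.

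The other investigator ratings among the clinical endpoints, the in-person mMASI and the investigator GAIS, are openly what they are. The quartile score differs because it stands inside the endpoint that describes blinded reading. A reader of the results could reasonably count it as blinded support for the laser's added effect when it may be no such thing.

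**Working it through.** The documents give no figure on rater bias, so there is nothing to reproduce. The check is textual.

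**Step 1. Does the protocol use *investigator* for the blinded readers?** Three places keep the roles apart.

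| Place in the Protocol | Investigator | Blinded readers |
|---|---|---|
| Study population (under Objectives) | grades at visits 1 and 4, with the subject | review photographs from visits 1 and 4 |
| Intended Use of the Data | examines follow-up photographs | also examine them, named separately |
| Criteria of Evaluation, GAIS bullet and photographic bullet | rates GAIS, as does the subject | rate the photographic mMASI |

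Read consistently with these, the investigator who gives the quartile score is not one of the two blinded dermatologists.

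**Step 2. Would that investigator know the lasered side?** The side to be lasered is identified and mapped at visit 1 (Procedure, Visit 1). The investigator is in the laser room (Laser Parameters), and one investigator evaluates a given subject throughout (Clinical Evaluations). No sham exposure of the other side and no masking of the investigator is described. Knowledge of the side is an inference from these statements, but a strong one.

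**Step 3. Is the score photographic, and is it compared between sides?** Neither is stated. That it is read from photographs follows from its place in the bullet. That sides would be compared follows from the hypothesis of greater improvement with the combination than with cysteamine alone. Both are inferences.

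**Step 4. What else is affected?** Nothing in the blinded reading itself. The photographic mMASI is assigned to the two blinded dermatologists whatever happens to the quartile score.

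**Step 5. Can the blinded readers give the score instead?** Yes. They already compare visit 1 and visit 4 photographs. The Photographs section provides left, right and front views, so images of each side exist. The extra load is subjects × sides × readers: 20 × 2 × 2 = 80 ratings, or 25 × 2 × 2 = 100 at the upper enrolment given under Sample Size Calculation.

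**The case against.** **The word may be loose.** The lead-in and the first endpoint say *treating physician* for the person who treats, so *investigator* in the photographic bullet might mean the blinded physician readers, as opposed to the subject. This cannot be excluded, and the finding therefore rests on the most natural reading and not on an explicit statement. If the loose reading is the intended one, the sentence still names the wrong role and the same edit puts it right.

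**The same-investigator rule is about visits.** It governs clinical scoring done before any treatment at a visit, and the scales that follow it are wrinkling, roughness and mottled hyperpigmentation. It does not say who reads photographs. That stands. It is used here only to show that the investigator has continuing, unmasked contact with the subject.

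**Other ratings are at least as exposed.** The in-person mMASI and investigator GAIS carry the same expectation risk, and reporting an investigator rating beside a blinded one is common. That is fair. What is particular to the quartile score is its placement among blinded assessments.

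**Two stronger readings go too far.**

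- A reader might infer that the Study population text, which promises blinded photographic evaluation, is contradicted. It is not. The blinded photographic mMASI fulfils it, the same text also plans investigator grading, and Intended Use of the Data openly plans examination of photographs by both.
- A reader might put a false-positive rate on the bias. With 20 pairs, a two-sided 5% paired t-test and an assumed SD of 1 category for the difference between sides, an assumed leaning of 0.1 to 0.5 category gives rejection rates of about 7% to 56% when the laser has no effect. The leaning, the SD and the test on this ordinal score are all assumptions. The width of the range only restates them and supports no claim about this trial.

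**Conclusion.** The point holds as a minor one. On the most natural reading, the quartile improvement score comes from a rater who knows the lasered side, while its position invites the reader to treat it as blinded. Any comparison of sides on it would be open to expectation bias.

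This rests on three inferences: that *investigator* carries its usual meaning in the protocol, that the investigator knows the side, and that the score is compared between sides. The size of any bias cannot be stated from the documents.

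Who rates an endpoint, and whether that person is masked, is a matter of trial conduct that the protocol itself has fixed, so it is not something simply left to a statistical analysis plan.

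**What to change.** In the third clinical endpoint under Criteria of Evaluation, replace the investigator quartile score with wording such as: *The two blinded dermatologists will also give a quartile improvement score from baseline to week 12, separately for each side of the face, from the visit 1 and visit 4 photographs, at the same reading as the photographic mMASI and without knowledge of which side was lasered.*

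If an investigator quartile score is still wanted, list it as a separate item and report it as unblinded and supportive.

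The cost is a short edit to one endpoint and the 80 to 100 extra ratings worked out above, at a reading session already planned. No new readers or images are needed.

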#### Visit 4 (Week 12)

- Assess side-effects of treatment
- See how tall subject is and how much subject weighs
- Take photos of face
- Perform grading of melasma
- Post-treatment questionnaire
- Evaluation of photos comparing visit 1 and 4 to be performed

**Risks and Discomforts:** Blistering, edema, erythema and local pain are typical reactions to laser treatment. A lesser possibility exists for hyperpigmentation, hypopigmentation scarring, and/or infection. These conditions may or may not resolve over time. As with any method of tissue destruction, there is a risk of infection and of scarring, which is minimized with proper wound care. Eye injury due to the use of the laser is a risk to the subject as well as the operator. The subjects may experience partial or permanent hair reduction. Risks of the topical include temporary irritation, burning or heating up sensation that resolves within 30 minutes

**Benefits:** The subjects may or may not show improvement of melasma on the treatment sites. There is no guarantee of success.

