**Table. Determination of the Modified MASI (mMASI) Score**

Location of Melasma	Scoring a	Calculation for Total Score b
Forehead	(0.3) (A) (D)	
Left malar	(0.3) (A) (D)	Forehead mMASI Score + Left Malar mMASI Score + Right Malar mMASI Score + Chin mMASI Score = Total mMASI Score
Right malar	(0.3) (A) (D)	
Chin	(0.1) (A) (D)	

Abbreviation: MASI, Melasma Area and Severity Index.

a Scoring system: A, Area of involvement rated 0 to 6: 0 indicates absent; 1, <10%; 2, 10% to 29%; 3, 30% to 49%; 4, 50% to 69%; 5, 70% to 89%; 6, 90% to 100%. D, Darkness rated 0 to 4: 0 indicates absent; 1, slight; 2, mild; 3, marked; 4, severe.

b Total mMASI score range is 0 to 24 and calculated by adding scores for 4 areas of the face.

Safety Endpoints:

- Incidence of adverse safety events during the treatment and follow up period
- Subject assessment of pain and discomfort associated with treatments using an 11-point visual assessment scale (VAS) pain score

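### The additional quartile improvement score cannot register worsening: a side that darkens scores the same as an unchanged side, which can distort a between-side comparison in either direction

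*Protocol*

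**What the plan says.** Under Criteria of Evaluation (Study Endpoints), the bullet on photographic assessment first has two blinded dermatologists who "will assess improvement in melasma by mMASI score". It then continues: "In addition, an investigator quartile improvement score from baseline to week 12", with the scale given as "0 – 0%, no improvement; 76%-100% - very significant improvement". The middle categories are not written out. The bullet does not say that this score is given for each side, that it is compared between sides, or that its rater is blinded.

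The neighbouring bullet on the GAIS does provide for deterioration: "The rating categories used on this scale will be “worse” “no change” “improved", followed by two higher grades. The investigator and the subject rate it.

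On risk, the Risks and Discomforts paragraph says of the laser: "A lesser possibility exists for hyperpigmentation, hypopigmentation scarring, and/or infection". Of the cream it says: "Risks of the topical include temporary irritation, burning or heating up sensation that resolves within 30 minutes". Under Study population, hyperpigmentation is among the side effects recorded at visits 2, 3 and 4.

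On the standing of the score, the Background states for the primary objective: "This efficacy will be assessed using modified Melasma Area and Severity Index (mMASI) scores", together with Investigator Global Assessments. The quartile score is not named there.

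**The concern.** The trial treats one randomly selected side of each face with laser and both sides with cysteamine, and its hypotheses concern the difference between sides. An improvement score with its floor at no improvement discards part of that difference. Worsening is coded as no change, while improvement is graded in four further steps (if the unprinted middle categories are the usual quarters).

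This matters more here than in many trials because darkening of the skin is both a listed laser risk and a deterioration in the outcome itself. On the Protocol's own risk lists, a treatment-related cause of darkening exists only on the lasered side. The Background also describes melasma as chronic or relapsing, so the cysteamine-only side can worsen too. If the score is used to compare sides, a reader of the result cannot tell a side that stayed the same from one that got worse.

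**Working it through.** **The plan's own figure.** The Protocol attaches no number to this score. Its sample size of 20 subjects (up to 25 with dropout) is stated without an effect size or standard deviation and has no bearing on the scale. It is used below only as the number of pairs.

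**Step 1: what the floor does.** Let L and C be the category changes on the lasered and the control side on a scale that allows worsening, and let L⁺ and C⁺ be the same values with everything below 0 set to 0. Then

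bias = E[L⁺ − C⁺] − E[L − C] = (mean worsening removed on the laser side) − (mean worsening removed on the control side).

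The floor acts on both sides, so the sign depends on which side has more worsening to remove.

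**Step 2: simple rates.** Assume each darkened side worsens by exactly one category, with proportions p_L and p_C. Then bias = p_L × 1 − p_C × 1. The rates are assumptions, since the Protocol gives none.

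| p_L | p_C | bias (categories) |
|---|---|---|
| 10% | 0% | +0.10, toward the laser |
| 20% | 0% | +0.20, toward the laser |
| 10% | 10% | 0 |
| 10% | 20% | −0.10, against the laser |

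**Step 3: a graded version.** Assume normal percent improvement on each side, 25-point categories, and a reference scale with matching categories below zero (1,000,000 simulated pairs).

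| Laser mean (SD) | Control mean (SD) | Darkened, laser / control | Difference, full scale | Difference, floored | bias |
|---|---|---|---|---|---|
| 25 (20) | 25 (20) | 10.5% / 10.5% | 0.00 | 0.00 | 0.00 |
| 25 (35) | 25 (20) | 23.7% / 10.5% | −0.15 | +0.07 | +0.22 |
| 25 (20) | 25 (35) | 10.5% / 23.8% | +0.15 | −0.07 | −0.22 |
| 35 (20) | 20 (20) | 4.0% / 15.8% | +0.72 | +0.59 | −0.13 |

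In the second and third rows the floor reverses the sign of the difference, once in each direction. The last row matches the Protocol's hypothesis of greater improvement with laser, and there the floor understates the laser effect.

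**Step 4: a significance illustration with 20 pairs.** The counts and the choice of an exact two-sided sign test are assumptions. Let 8 pairs favour the laser, 9 tie, and 3 have one darkened side next to an unchanged one.

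- Floored score: the 3 pairs become ties, leaving 8:0, p = 2 × 1/256 = 0.008.
- If the 3 darkened sides were lasered, a worse category gives 8:3, p = 2 × (165 + 55 + 11 + 1)/2048 = 464/2048 = 0.227.
- If the 3 darkened sides were control sides, a worse category gives 11:0, p = 2 × 1/2048 = 0.001.

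The same floored result of 8:0 is compatible with both. A darkened side paired with an improved side keeps its direction under the floor; only the size of that difference is understated.

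**Step 5: where darkening can still be seen.** "Total mMASI score range is 0 to 24", built from area and darkness, so mMASI rises when skin darkens, and it is read from photographs by blinded dermatologists. The GAIS has a category for deterioration. Hyperpigmentation is recorded as a side effect at three visits.

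**The case against.** The strongest reply is that the trial is not blind to darkening. Blinded photographic mMASI stands in the same bullet and can move in both directions, the GAIS has a lower category, and side effects are recorded separately. The quartile score is an addition, and only its two end anchors are printed, so the rating form may contain more. This largely stands, and it is why the point is a small one. Two limits remain. The printed lower anchor is explicit, so a scale followed as written has nothing beneath it. The mMASI table scores the left and right malar areas separately, but gives the forehead and chin one score each and defines no total per side, so it compensates only in part on a between-side question.

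A reader might infer that the floor biases the comparison toward the laser, because the listed darkening risk belongs to the laser. The documents do not support that as a certain result. The floor removes worsening on both sides, melasma can relapse on either, and no darkening rates are given. Steps 2 to 4 show zero and opposite effects under equally open assumptions.

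A reader might also infer that this is the one blinded measure and that only unblinded raters could report worsening. The text does not say that either. It calls the quartile score an investigator score, and it has the blinded reviewers rate mMASI.

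**Conclusion.** The defect is real and narrow. As printed, the quartile score cannot register worsening, so a darkened side and an unchanged side share a category. If the score is compared between sides, as the split-face design implies but the endpoint text does not state, the comparison can be distorted toward the laser or against it, according to which side darkens more. Under the assumed scenarios tabulated above, the shift runs from −0.22 to +0.22 category, and the real sign and size cannot be derived from the Protocol. The p-values show how much a few hidden pairs can matter with 20 patients; they do not predict what will happen. The effect is confined to this additional endpoint and does not touch the measures named for primary efficacy. Low priority, but worth correcting before the photographs are rated.

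**What to change.** Add one category below zero to the quartile score (for example −1, worse than baseline). State that the blinded photographic reviewers already planned will rate it for each side, and keep the new category in any paired ordinal comparison instead of merging it with zero. A single category restores the direction of change. It does not grade how far a side has worsened, and two sides that both darken would still tie; further negative categories would be needed if that matters to the sponsor.

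The cost is one line on the rating form and a sentence on who rates and for which side. The score will look slightly less favourable if darkening occurs. Making the change after rating would mean reading the photographs again.
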